- **For cohort 9, diagnosis of diabetes is not excluded provided diabetes is well-controlled according to treating physician's assessment and discretion, and the subject is on stable doses of diabetes medications for at least 6 weeks prior to enrollment**

206 Planned elective surgery to occur at any time from screening visit through the end of treatment visit for cohorts 1 to 7, and through the end of study visit for cohorts 8 and 9

207 Estimated glomerular filtration rate (eGFR)  $\leq$  60 mL/min/1.73 m^2, as defined by the local laboratory, at screening

208 Triglycerides  $\geq$  5.65 mmol/L (ie, 500 mg/dL) at screening

209 History or clinical evidence of liver dysfunction, including total bilirubin  $>$  upper limit of normal (ULN) or ALT or AST  $>$  1.1 ULN of the laboratory's reference at screening or at day -1 for cohorts 1 to 5, or day -3 to -1 for subjects not on statin in cohorts 6 to 9. For subjects on stable dose of statin in cohorts 6 to 9, ALT or AST  $>$  1.5 ULN of the laboratory's reference at screening or at day -3 to -1.

210 History or clinical evidence of bleeding diathesis or any coagulation disorder, including prothrombin time (PT), activated partial thromboplastin time (aPTT), thrombin time (TT), or platelet count outside of the laboratory's normal reference range at screening

211 **For cohorts 1 to 8, history or clinical evidence of diabetes mellitus, including a fasting glucose  $\geq$  125 mg/dL (6.9 mmol/L) at screening**

212 History or clinical evidence of peripheral neuropathy

213 History of malignancy of any type, other than in situ cervical cancer or surgically excised non-melanomatous skin cancers occurring more than 5 years prior to randomization

214 Positive results for human immunodeficiency virus (HIV) antibodies, hepatitis B surface antigen (HBsAg), hepatitis B core antibody (HBcAb), or hepatitis C virus

ribonucleic acid (RNA). For hepatitis C, hepatitis C antibody (HepCAb) testing is done at screening, followed by hepatitis C virus RNA by polymerase chain reaction (PCR) if hepatitis C antibody is positive.

215 Subject was previously enrolled in this study or has been previously exposed to AMG 890

216 Use of any herbal medicines, vitamins or supplements known to affect lipid metabolism (eg, fish oils > 4000 mg/day, red yeast rice extract), within 30 days prior to dosing on day 1

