#### 9.4.1 Criteria for Permanent Withholding of Amgen Investigational Product and Other Protocol-required Therapies due to Potential Hepatotoxicity

Investigational product and other protocol-required therapies, as appropriate, should be discontinued permanently and the subject should be followed according to the recommendation in the [Appendix A](#) (Additional Safety Assessment Information) for possible drug-induced liver injury (DILI), if ALL the criteria below are met:

- TBIL > 2x upper limit of normal (ULN) or INR > 1.5
- AND increased AST or ALT from the relevant baseline value as specified below:

| Baseline AST or ALT value | AST or ALT elevation |
|---------------------------|----------------------|
| < ULN                     | > 3x ULN             |

- AND no other cause for the combination of the above laboratory abnormalities is immediately apparent; important alternative causes for elevated AST/ALT and/or TBIL values include, but are not limited to:
  - Hepatobiliary tract disease
  - Viral hepatitis (eg, Hepatitis A/B/C/D/E, Epstein-Barr Virus, cytomegalovirus, herpes simplex virus, varicella, toxoplasmosis, and Parvovirus)
  - Right sided heart failure, hypotension or any cause of hypoxia to the liver causing ischemia.
  - Exposure to hepatotoxic agents/drugs or hepatotoxins, including herbal and dietary supplements, plants and mushrooms
  - Heritable disorders causing impaired glucuronidation (eg, Gilbert's Syndrome, Crigler-Najjar syndrome) and drugs that inhibit bilirubin glucuronidation (eg, indinavir, atazanavir)
  - Alpha-1 antitrypsin deficiency
  - Alcoholic hepatitis
  - Autoimmune hepatitis
  - Wilson's disease and hemochromatosis
  - Nonalcoholic Fatty Liver Disease including Steatohepatitis (NASH)
  - Non-hepatic causes (eg, rhabdomylosis, hemolysis)

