### **12.1.2        Serious Adverse Events**

A serious adverse event is defined as an adverse event that meets at least 1 of the following serious criteria:

- fatal
- life threatening (places the subject at immediate risk of death)
- requires in patient hospitalization or prolongation of existing hospitalization
- results in persistent or significant disability/incapacity
- congenital anomaly/birth defect
- other medically important serious event

An adverse event would meet the criterion of "requires hospitalization," if the event necessitated an admission to a health care facility (eg, overnight stay).

If an investigator considers an event to be clinically important, but it does not meet any of the serious criteria, the event could be classified as a serious adverse event under the criterion of "other medically important serious event." Examples of such events could include allergic bronchospasm, convulsions, blood dyscrasias, drug induced liver injury (DILI) (see [Appendix A](#) for DILI reporting criteria), or events that necessitate an emergency room visit, outpatient surgery, or urgent intervention.

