#### **12.2.1.2 Reporting Procedures for Serious Adverse Events**

The investigator is responsible for ensuring that all serious adverse events observed by the investigator or reported by the subject that occur after signing of the informed consent through the end of study visit (last visit where data for primary endpoints are collected) are recorded in the subject's medical record and are submitted to Amgen. All serious adverse events must be submitted to Amgen within 24 hours following the investigator's knowledge of the event via the Event eCRF and using the paper based Serious Adverse Event Report (SAER) Form (see [Table 10](#) and [Appendix B](#)).

The investigator must assess whether the serious adverse event is possibly related to the investigational product (AMG 890 or placebo). Relatedness means that there are facts or reasons to support a relationship between investigational product and the event.

The investigator must assess whether the serious adverse event is possibly related to any study mandated activity (eg, administration of investigational product, protocol-required therapies, use of medical device(s) and/or procedure (including any screening procedure(s)).

The investigator is expected to follow reported serious adverse events until stabilization or reversibility.

New information relating to a previously reported serious adverse event must be submitted to Amgen. All new information for serious adverse events must be sent to Amgen within 24 hours following knowledge of the new information. If specifically requested, the investigator may need to provide additional follow-up information, such as discharge summaries, medical records, or extracts from the medical records.

Information provided about the serious adverse event must be consistent with that recorded on the Event eCRF.

If a subject is permanently withdrawn from protocol-required therapies because of a serious adverse event, this information must be submitted to Amgen.

To comply with worldwide reporting regulations for serious adverse events, the treatment assignment of subjects who develop serious, unexpected, and related adverse events may be unblinded by Amgen before submission to regulatory authorities.

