#### Drug-induced Liver Injury Reporting & Additional Assessments

##### Reporting

To facilitate appropriate monitoring for signals of DILI, cases of concurrent AST or ALT and TBIL and/or INR elevation according to the criteria specified in Section 9.4 require the following:

- The event is to be reported to Amgen as a serious adverse event within 24 hours of discovery or notification of the event (ie, before additional etiologic investigations have been concluded)
- The appropriate eCRF (eg, Event eCRF) that captures information necessary to facilitate the evaluation of treatment-emergent liver abnormalities is to be completed and sent to the Amgen.

Other events of hepatotoxicity and potential DILI are to be reported as serious adverse events if they meet the criteria for a serious adverse event defined in Section 12.2.1.2.

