##### Additional Clinical Assessments and Observation

All subjects in whom investigational product(s) or protocol-required therapies is/are withheld (either permanently or conditionally) due to potential DILI as specified in Section 9.4 or who experience AST or ALT elevations  $> 3 \times$  ULN or 2-fold increase above baseline values for subjects with evaluated values before drug must undergo a period of “close observation” until abnormalities return to normal or to the subject’s baseline levels. Assessments that are to be performed during this period include:

- Repeat AST, ALT, ALP, bilirubin (total and direct), and INR within 24 hours
- In cases of TBIL  $> 2 \times$  ULN or INR  $> 1.5$ , retesting of liver tests, bilirubin (total and direct), and INR is to be performed every 24 hours until laboratory abnormalities improve

- Testing frequency of the above laboratory tests may decrease if the abnormalities stabilize or the investigational product(s) or protocol-required therapies has/have been discontinued AND the subject is asymptomatic.
- Initiate investigation of alternative causes for elevated AST or ALT and/or elevated TBIL. The following are to be considered depending on the clinical situation:
  - Complete blood count (CBC) with differential to assess for eosinophilia
  - Serum total immunoglobulin IgG, Anti-nuclear antibody (ANA), Anti Smooth Muscle Antibody, and Liver Kidney Microsomal antibody 1 (LKM1) to assess for autoimmune hepatitis
  - Serum acetaminophen (paracetamol) levels
  - A more detailed history of:
    - Prior and/or concurrent diseases or illness
    - Exposure to environmental and/or industrial chemical agents
    - Symptoms (if applicable) including right upper quadrant pain, hypersensitivity-type reactions, fatigue, nausea, vomiting and fever
    - Prior and/or concurrent use of alcohol, recreational drugs and special diets
    - Concomitant use of medications (including non-prescription medicines and herbal and dietary supplements), plants, and mushrooms
  - Viral serologies
  - CPK, haptoglobin, LDH, and peripheral blood smear
  - Appropriate liver imaging if clinically indicated
- Appropriate blood sampling for pharmacokinetic analysis if this has not already been collected
- Hepatology consult (liver biopsy may be considered in consultation with an hepatologist)

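### The Section 9.4.1 liver rule sets no AST/ALT threshold for a raised baseline, so a subject admitted with both enzymes at or above ULN cannot literally trigger the mandatory 24-hour DILI report (minor)

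*Protocol*

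**What the plan says.** **The liver rule.** Protocol Section 9.4.1 calls for permanent discontinuation and DILI follow-up when every one of three conditions holds: TBIL > 2x ULN or INR > 1.5; an enzyme condition, "AND increased AST or ALT from the relevant baseline value as specified below"; and no other immediately apparent cause. The table attached to the enzyme condition has one row: baseline AST or ALT < ULN, elevation > 3x ULN.

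**Who is admitted.** Exclusion Criterion 209 (Section 7.2) excludes ALT or AST above 1.1x ULN for cohorts 1 to 5 and for non-statin subjects in cohorts 6 to 9. A second limit, opening "For subjects on stable dose of statin in cohorts 6 to 9, ALT or AST", is set at 1.5x ULN.

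**What the rule triggers.** Appendix A says that concurrent elevations "according to the criteria specified in Section 9.4 require the following". The first requirement is: "The event is to be reported to Amgen as a serious adverse event within 24 hours of discovery or notification of the event", with the clarification that this means "before additional etiologic investigations have been concluded".

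**What exists outside the rule.** Appendix A also says that other hepatotoxicity and potential DILI events are reported as serious if they meet the general definition. It sets close observation separately, at AST or ALT > 3x ULN or a "2-fold increase above baseline values for subjects with evaluated values before drug" (where evaluated presumably means elevated). Section 12.1.2 lists DILI among examples for which "the event could be classified as a serious adverse event under the criterion of" other medical importance. Section 12.2.1.2 adds that "All serious adverse events must be submitted to Amgen within 24 hours following" the investigator's knowledge of them.

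**The concern.** The eligibility rule and the liver rule do not cover the same range of baselines. Exclusion 209 lets in subjects between 1.0x and 1.1x ULN, or between 1.0x and 1.5x ULN on a statin. The 9.4.1 table has no row for them. If both enzymes start at or above ULN, the subject matches nothing in the table, the enzyme condition cannot be satisfied, and a rule that needs every condition cannot be met.

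The result runs the wrong way: the subject with the less normal starting liver tests has the weaker reporting rule. AMG 890 acts in the liver, and cohort 9 combines the highest dose (675 mg) with at least 6 statin subjects. What would be lost is the one route that classes the event as serious by specified criteria and requires the report before the work-up of causes is finished.

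**Working it through.** The plan gives no figure to reproduce here, so the check is to run test subjects through the written rules and then size the gap.

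**Step 1. Apply the rules.** Values are multiples of ULN. After dosing, each subject has both enzymes at the stated level, TBIL 3x ULN, INR 1.6 and no other cause.

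| Baseline ALT / AST | Statin | Admitted by 209 | Later AST and ALT | 9.4.1 met | Close observation |
|---|---|---|---|---|---|
| 0.9 / 0.9 | yes | yes | 3.1, 8 or 20 | yes | yes |
| 1.4 / 0.9 | yes | yes | 3.1, 8 or 20 | yes, through the enzyme that started at 0.9 | yes |
| 1.4 / 1.3 | yes | yes | 3.1, 8 or 20 | **no** | yes |
| 1.05 / 1.05 | no | yes | 3.1, 8 or 20 | **no** | yes |
| 1.0 / 1.0 | yes | yes | 3.1, 8 or 20 | **no** (the inequality is strict) | yes |

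The gap needs both enzymes at or above ULN at baseline. One normal enzyme is enough to keep a route into the rule. The height of the later values makes no difference.

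**Step 2. Size it.** Cohorts 1 to 8 are closed to enrolment, so the practical case is mainly cohort 9: 8 planned subjects (6 AMG 890, 2 placebo), at least 6 of them on a statin. With 2 placebo subjects, 4 to 6 of those 6 would be on AMG 890.

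The documents give neither the share of subjects with both enzymes raised nor the liver event rate. Both ranges below are assumptions.

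- Share of statin subjects with both enzymes at or above ULN, 2% to 10%. Expected number: 6 x 0.02 = 0.12 to 6 x 0.10 = 0.6.
- Chance of at least one such statin subject: 1 - 0.98^6 = 11.4% to 1 - 0.90^6 = 46.9%.
- Probability per subject of an otherwise qualifying liver event, 0.1% to 1%. Expected missed triggers: 0.12 x 0.001 = 0.00012 to 0.6 x 0.01 = 0.006.

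**Step 3. Test the fix.** With > 3x ULN applied to every baseline, the fold rise at the threshold is 3.0/1.0 = 3.0, 3.0/1.1 = 2.7 and 3.0/1.5 = 2.0. No admitted subject would trigger on less than a doubling.

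**The case against.** **The row may exist.** A baseline-by-elevation table with one row is odd, the lead-in speaks of a relevant baseline, and Appendix A elsewhere foresees raised baselines. A second row could have been lost when the PDF was read. This stands as a caveat and cannot be settled from the text. A drafting omission is also plausible: the summary for Amendment 3 records that criterion 209 was changed to set the 1.5x ULN limit for statin subjects, and the liver table may not have been revisited.

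**Section 9.4 cites FDA guidance on liver injury.** True, but the protocol takes no threshold from it for raised baselines, so a site reading the protocol has nothing to apply.

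**The rule is not purely mechanical.** This stands. Section 9.4.1 already asks whether another cause is apparent, and other hepatotoxic drugs are on its list of alternatives. The contrast is between a specified trigger with some judgement and a general route with more.

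**Other routes remain.** This also stands. Appendix A's sentence on other potential DILI events makes reporting mandatory once the event is judged serious, and DILI is a named example. That route is weaker in one respect: Section 12.1.2 refers back to Appendix A for DILI reporting criteria, which leads again to Section 9.4.

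**Stronger readings.** A reader might infer that liver injury in these subjects would go undetected or unreported. The documents do not support that. Close observation is compulsory above 3x ULN whatever the baseline, TBIL > 2x ULN brings 24-hourly retesting, potential DILI must be captured in CRFs, laboratory results are signed off by the investigator or a designee (Section 10.3), and the unblinded Medical Monitor reviews data continuously (Section 9.2.4.2). Nor would a subject wrongly keep receiving AMG 890, because there is only one dose. Stopping a statin is left to what is appropriate even when the rule is met.

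**Conclusion.** Wrong as written, but minor, and subject to confirming that no table row was lost. A subject whom Exclusion 209 admits with both AST and ALT at or above ULN cannot literally satisfy 9.4.1, and so falls outside the mandatory 24-hour DILI report tied to it. The loss is confined to that reporting trigger.

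Under the assumed ranges, the expected number of missed triggers in cohort 9 is at most about 0.006. That counts lost triggers, not unreported events, because it gives no credit to the general serious-event route. The 11% to 47% range is the chance that cohort 9 contains such a statin subject and should not be read as the chance of a missed report. No endpoint, analysis set or estimate changes. The reason to act is that a stated safety rule gives the wrong answer for subjects the protocol admits, not that cases are expected.

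**What to change.** First check the 9.4.1 table in the source PDF. If it has a row for raised baselines, nothing needs changing.

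If it does not, delete the < ULN baseline condition so that AST or ALT > 3x ULN applies regardless of baseline. This matches the > 3x ULN close-observation threshold in Appendix A. Adding a row based on Appendix A's 2-fold rule would also close the gap, but at a baseline of 1.1x ULN it would act at 2 x 1.1 = 2.2x ULN, a lower absolute level than for a normal baseline. The single threshold is simpler.

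The at-least-doubling property assumes that the central-laboratory baseline (Section 10.2) agrees with the local result used for eligibility. A central value above 1.5x ULN would make 3x ULN less than a doubling.

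The cost is one table edit, in a clarification letter or the next amendment, with no added tests or visits. The downside is at most an occasional extra expedited report.

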## 9.5 Concomitant Therapy

Throughout the study, Investigators may prescribe any concomitant medications or treatments deemed necessary to provide adequate supportive care except for those listed in Section 12.

Concomitant therapies are to be collected from informed consent through the end of treatment visit for cohorts 1 to 7, and through the EOS for cohorts 8 and 9. Collect therapy name, indication, dose, unit, frequency, route, start date, and stop date.

Concomitant medications will not be collected after the end of treatment visit for any subjects with additional safety follow-up in cohorts 1 to 7.

## 9.6 Alcohol and Tobacco Restrictions

Subjects must limit alcohol consumption throughout the course of study participation (refer to Exclusion Criteria, Section 7.2). Alcohol is prohibited for approximately 48 hours prior to admission to the research facility (day -1 for cohorts 1 to 5 and the sentinel pair of cohort 9; day -3 to -1 for cohorts 6 to 9 [other than the sentinel pair]), and throughout the residency period. Alcohol consumption is limited to no more than 2 drinks per day for males and 1 drink per day for females for the duration of the study (1 drink is equivalent to 12 ounces of regular beer, 8 to 9 ounces of malt liquor, 5 ounces of wine or 1.5 ounces of 80 proof distilled spirits).

---

Only non-nicotine or non-tobacco using subjects should be enrolled. Subjects should not have used any nicotine or tobacco containing products within the last 6 months prior to screening. Subjects must abstain from nicotine or tobacco containing products (including but not limited to: snuff, chewing tobacco, cigars, cigarettes, electronic cigarettes, pipes, or nicotine gum or nicotine patches) throughout the screening period and for the duration of the study.

**9.7                   Exercise**

Subjects should abstain from strenuous exercise for 72 hours before each blood collection for clinical laboratory tests. Subjects may participate in light recreational activities during study.

**9.8                   Product Complaints**

A product complaint is any written, electronic or oral communication that alleges deficiencies related to the identity, quality, durability, reliability, safety, effectiveness, or performance of a drug(s) or device(s) after it is released for distribution to market or clinic by either Amgen or by distributors and partners for whom Amgen manufactures the material.

This includes any drug(s), device(s), or combination product(s) provisioned and/or repackaged or modified by Amgen. Drug(s) or device(s) includes investigational product, AMG 890 or placebo.

Any product complaint(s) associated with the investigational product supplied by Amgen are to be reported according to the instructions provided in the IPIM.

**9.9                   Excluded Treatments, Medical Device Use, and/or Procedures During Study Period**

Use of any over-the-counter or prescription medications within 14 days or 5 half-lives (whichever is longer), prior to dosing on day 1 and during the study is not permitted, unless to treat an adverse event. Additionally, use of any herbal medicines, vitamins or supplements known to affect lipid metabolism (eg, fish oils > 4000 mg/day, red yeast rice extract), within 30 days prior to dosing on day 1 and for the duration of the study is not permitted.

Accepted exceptions are:

- Acetaminophen (or paracetamol) up to 2 grams per day for analgesia
- Hormone replacement therapy (eg, estrogen, thyroid) provided subject is stable on replacement therapy

- Medication for the management of arterial hypertension, including but not limited to angiotensin-converting enzyme inhibitors, angiotensin-receptor blockers, calcium channel blockers, beta blockers, or low-dose thiazides, provided it is stable (ie, no change in drug or dose) for at least 6 weeks prior to enrollment, as defined in Exclusion Criterion 219 (Section 7.2)
- For cohorts 6 to 9, at least 6 subjects in each cohort must be on a stable dose of the same statin for at least 6 weeks prior to enrollment, and plan to remain on a stable dose (ie, no change in medication or dosage) for the duration of the study, as defined in Inclusion Criterion 103 (Section 7.1)
- For cohorts 6 to 9, ezetimibe is permitted as long as subjects have been on a stable dose for at least 6 weeks prior to enrollment, and plan to remain on the same dose for the duration of the study, as defined in Exclusion Criterion 219 (Section 7.2)
- For cohorts 6 to 9, antiplatelet therapy (low-dose acetylsalicylic acid, clopidogrel or ticagrelor) is permitted as long as subjects have been on a stable dose for at least 6 weeks prior to enrollment, and plan to remain on the same dose for the duration of the study, as defined in Exclusion Criterion 219 (Section 7.2)
- For cohorts 6 to 9, medication used to manage chronic conditions not excluded by exclusion criteria, provided subjects have been on a stable dose for at least 6 weeks prior to enrollment and plan to be on the same dose for the duration of the study. Medication must be reviewed and approved by the investigator, and acknowledged by the Amgen Medical Monitor. Written documentation of this review and Amgen acknowledgement is required for subject participation, as defined in Exclusion 219 (Section 7.2)
- **For cohort 9, medication used to manage diabetes not excluded by other exclusion criteria, provided subjects have been on a stable dose for at least 6 weeks prior to enrollment and plan to be on the same dose for the duration of the study. Medication must be reviewed and approved by the investigator, and acknowledged by the Amgen Medical Monitor. Written documentation of this review and Amgen acknowledgement is required for subject participation, as defined in Exclusion 219 (Section 7.2).**

All herbal supplements and nutritional supplements (with the exception of those known to affect lipid metabolism, excluded above) should not be taken within 30 days prior to dosing on day 1 and should not be used during the study, unless reviewed and approved by the investigator and Amgen Medical Monitor. Written documentation of this review and Amgen acknowledgement is required for subject participation.

Any changes regarding concomitant medications should be recorded on the subject's source documents and the CRF along with the reason for the change.

---

